7.3 Special instructions and definitions of assessments

7.3.1 Randomisation

Randomisation will occur at Day 0 of the study. Patients will be randomised at a 1:1 ratio to one of the two treatment group DFP or DFX. The randomisation list will be determined centrally before the study start.

Other details about randomisation are provided in **Section 6.6**.

7.3.2 Informed Consent

As subjects enrolled in this study are below the legal age and cannot consent for themselves, signed Informed Consent Form will be obtained from both parents, legal guardian, or person with power of attorney. Additionally, the subject's assent will also be obtained if he or she is able to understand the nature, significance, and risks associated with the study.

As recommended by the European framework (Directive 2001/20/EC; Additional protocol on biomedical research, 2005; Ethical Recommendations, 2008), full comprehensive information will be given from the primary caregiver to all the legal representatives as well as the potentially eligible children for the trial before the written full informed consent.

Written and oral information will be given in language and wording appropriate to age, psychological and intellectual maturity and taking into account the cultural and linguistic differences. Information will be presented clearly, using short sentences and either avoiding or explaining all technical terms. They have to deal with:

- the rationale and objectives of the study;
- possible risks and potential and direct benefits associated with trial treatment;
- the arrangements for responding to AEs or the concerns of research participants;
- the nature, extent and duration of the procedures and, especially, the details of the extra burden caused by the trial;
- insurance information and the arrangements for fair compensation in the case of damage;
- the arrangements to ensure respect for private life and confidentiality of the individual data arising from the research;
- the arrangements for accessing information produced by the study and relevant to the participant;
- the rights and safeguard dictated by law for the child protection;

- the right to freely refuse or to withdraw from the trial at any time for any reason without any disadvantage or prejudice without reasoning the decision and without being subject to any liability and/or to any form of discrimination, in particular regarding his/her right to medical care.

Separate information sheets describing the study's objectives and procedures, elaborated in a form which will take into account the cultural and linguistic differences in the study population, will be provided to the parent/legal guardian prior to the submission of the Informed Consent Form. The parent/legal guardian will be provided an Informed Consent Form in his/her National language to be signed only upon agreement of the terms and conditions included in the document.

All the time necessary to freely decide the involvement of a subject in the clinical trial will be made available.

In addition, and in accordance with the "Ethical Considerations for Clinical Trials Performed in Children", Recommendations of the *ad hoc* group for the development of implementing guidelines for Directive 2001/20/EC relating to GCP in the conduct of clinical trials on medicinal products for human use, separate information sheets specifically elaborated for children and adolescents, in language and wording appropriate to age, psychological and intellectual maturity, and taking into account the cultural and linguistic differences, will be provided to each patients in order to inform him/her on the study's objectives and procedures and obtain his/her assent to the participation to the study.

According to the European Ethical Recommendations (2008), if the child's assent is not obtained, this should be documented in the Informed Consent Form which is signed by the parent/legal representative and investigator.

The Informed Consent Form must be signed and personally dated by the legal representative and the Investigator / Co-Investigator. The original copy of the signed forms will be retained with the source documents in the trial site and a copy will be given to the family/participant.

Upon parents' and/or participant's consent, a letter will be sent to the participant's primary care doctor informing him/her of the involvement of his/her young patient in the trial, the treatment, the concomitant other medicinal products not permitted.

Carers and participants are free to refuse to participate to the trial or withdraw their consent at any time and for every reason.

After the patient has entered the trial, the clinician must remain free to give alternative treatment to that specified in the protocol, at any stage, if he/she feels it to be in the best interest of the patient.

7.3.3 Inclusion/exclusion criteria

During the screening period (day-28 to day -7), the patient will execute examinations/evaluations allowing the assessment of inclusion/exclusion criteria set in **Section 5.1** and **Section 5.2**. Inclusion/exclusion criteria must be satisfied at the time of the washout visit (V2, day -7) before starting the wash-out period.

7.3.4 Pregnancy test

For females with childbearing potential a pregnancy test (β -HCG) will be carried out locally on serum during the screening period (V1) and at the end of treatment (V15). During the treatment of the study pregnancy testing (β -HCG) will be repeated if pregnancy is suspected.

CONFIDENTIAL

DEEP Consortium

DEEP2-Efficacy/Safety Study Protocol

Protocol No. DEEP-2

Fertile and sexually active male or female patients should be advised to use an approved method of contraception from time of enrolment (V1), throughout the course of the trial, and for 30 days following early termination or the last visit (V16).

In the situation where a female patient becomes pregnant, study medication must be stopped immediately and the patient is withdrawn from the study, and procedures outlined in **Section 16.5** must be followed.

Male patients must inform the Investigator if their female partner becomes pregnant during the trial or within one month after trial completion. Procedures outlined in **Section 16.5** must be followed. However, there will be no requirement for the male patient to be withdrawn from the trial.

The Investigator should counsel the patient, discuss the risks of continuing with the pregnancy and the possible effects on the foetus. Monitoring of the patient should continue until conclusion of the pregnancy, and the outcome should be transmitted to the Sponsor as well.

Approved methods of contraception will consist of the following for the purposes of this study or must follow local requirements:

- Oral contraceptive medications with condom or spermicide
- Hormonal implants with condom or spermicide
- Injectable contraceptive medications with condom or spermicide
- Condom used with spermicide.

If the hormonal contraception is used, it should have a Pearl index <1%.

[All statements in this section should apply without prejudice and fully respecting the ethical and religious habit of the concerned patient.]

7.3.5 Clinical physical examination

Clinical physical examination will be performed at each visit (V1 to V15) and at V16 (follow-up).

7.3.6 Medical history and current medical conditions

Anamnesis and medical history will be assessed at screening (V1). Significant findings must be included in the CRF. Current medical conditions will be also recorded at screening (V1) as part of the patient medical history.

7.3.7 Pharmacokinetics

Pharmacokinetic assessment will be performed in patients who complete the study. Last dose of the study treatments (DFP and DFX) must be administered in the clinic under supervision of qualified staff at the beginning of the visit V15 and time of administration must be recorded accordingly and reported in the CRF. A sample (2 mL) for the assessment of peak drug concentrations should be collected within 4 hours after dosing according to the sparse sampling scheme specified in the SPM.

7.3.8 Vital signs

Blood pressure and pulse rate will be assessed during screening (V1), at baseline (V3) and monthly thereafter at scheduled visits (V4 to V16) during the treatment and observation period. Systolic and diastolic blood pressure and pulse rate will be measured after the subject has rested in the sitting position for at least 3 minutes. Blood pressure should be assessed at the same arm each time.

7.3.9 Liver function history

For the comprehensive documentation of the patient's liver condition the following data will be collected at screening (V1): history of hepatitis, cirrhosis, results from liver biopsy, if available.

7.3.10 Heart function history

For the comprehensive documentation of the patient's heart condition any record documenting severe heart dysfunction and arrhythmia will be collected at screening (V1).

7.3.11 Liver MRI

Liver MRI will be assessed in all patients able to undergo the MRI evaluation without sedation (regardless of their treatment assignment) at day 0 (V3)±20 days and month 12 (V15)±20 days, adopting the MRI-based FerriScan® technology from Resonance Health Ltd.

Patients will be referred to an MRI Centre for a FerriScan evaluation by the investigator. The scan data acquired will be sent to the Resonance Health central processing facility by secure transmission. A quality controlled analysis process will provide a LIC report available for download by the MRI centre.

MRI instrument specifications: the process uses patented spin density projection R2-MRI imaging technology. Each MRI screening centre will be equipped with a MRI scanner with a field strength of 1.5 Tesla.

MRI instrument calibration verification: FerriScan will be provided as a service to MRI Centres selected after assessing the suitability of their scanners for the protocol.

A Service Agreement will be established with the MRI Centres, and an Instruction Manual will be provided on all aspects of the FerriScan analysis service. A Phantom Pack will be provided by Resonance Health Ltd to complete the validation and set-up process in the MRI centres. Scan data will be transmitted for analysis at the Resonance Health quality-controlled central processing facility. Once the Phantom Pack will be successfully scanned, the MRI Centre will receive confirmation that patient scanning may commence.

[figure not shown]
Data Analysis: MRI images will be captured and securely transmitted to the Resonance Health ISO9000 and ISO13485 accredited analysis facility. The patented FerriScan analysis procedure will produce a map of liver iron and will calculate a mean LIC measurement. Results will then be available for secure download within a target time of 48 hours.

Scan data will be transmitted to the Resonance Health service centre through a secure web-based portal. Only authorised persons from MRI facilities will then be able to track its progress through the FerriScan Analysis Service Tracking system (FAST).

A LIC report will be available for download within two working days.

Evaluation procedure: the MRI evaluation process is outlined in **Figure 2**.

Figure 2. MRI evaluation procedure.

7.3.12 Serum Ferritin

All the determinations relative to serum ferritin will be carried out on the same sample collection as haematology/biochemistry at screening, and at each monthly visits for evaluation at the local laboratory for patient clinical monitoring.

Additional serum ferritin determinations will be performed in blood collected in separate vials at V3, V6, V9, V12, V15 and will be evaluated in the centralised laboratory/ies as specified in the SPM. Central determination of ferritin will be performed also in case of withdrawal during the early termination visit. Central determinations will be used for formal analyses.

7.3.13 ECG

A standard 12-lead electrocardiogram (ECG) will be performed during screening (V1), at baseline (V3) and every 3 months during the treatment and observation period at scheduled visits (V6, V9, V12, V15). The same physician at the centre will interpret all ECGs to maintain consistency. The tracings will be measured, interpreted, dated, signed and must be filed in the hospital record. ECG tracings must show at least 5 R-R intervals, in order to allow proper calculations of the QT corrected times. The subject's number and initials, the date and actual time of the tracing, and "Study DEEP-2" must appear on each page of the tracing.

7.3.14 Cardiac MRI T2*

Cardiac MRI T2* will be assessed in patients above 10 years of age able to undergo the MRI evaluation without sedation (regardless of their treatment assignment) at day 0 (V3) \pm 20 days, at month 6 (V9) \pm 20 days and at month 12 (V15) \pm 20 days.

The Cardiac T2* imaging protocol and the analysis are provided at Resonance Health's central image analysis facility under its quality controlled environment.

Patients will be referred to an MRI Centre to acquire cardiac T2* images. The scan data acquired will be sent to the Resonance Health central processing facility by secure transmission. A quality controlled analysis process will provide a result report available for download by the MRI centre.

MRI instrument specifications: the MRI scanner with field strength of 1.5 Tesla will be equipped with a cardiac MRI package that includes:

- RF coil suitable for acquiring cardiac images
- ECG facility
- Single breath-hold, multi-echo T2* sequence with:
Total of 8 echo times

Minimum TE between 2 and 3 ms

Maximum TE between 16 and 23 ms

MRI instrument calibration verification: cardiac T2* image analysis will be provided as a service to MRI Centres selected after assessing the suitability of their scanner. Centres not equipped with a scanner or equipped with an unsuitable instrumentation will be referred to another equipped Centre.

A Service Agreement will be established with the MRI Centres, and an Instruction Manual will be provided on all aspects of the service.

Data Analysis: MRI images will be captured and securely transmitted to the Resonance Health ISO9000 and ISO13485 accredited analysis facility. Results will then be available for secure download within a target time of 48 hours.

Scan data will be transmitted to the service centre through a secure web-based portal. Only authorised persons from MRI facilities will then be able to track its progress through the system.

A cardiac MRI T2* report will be available for download within two working days

Evaluation procedure: the MRI evaluation process is outlined in Figure 2.

7.3.15 Urinalysis

Complete urinalysis and proteinuria assessed as urine protein/urine creatinine ratio on a fresh sample will be assessed at screening (V1), at baseline (V3) and monthly (V4 to V15) and weekly (\pm 7 days) during the first month after initiation or modification of therapy, as indicator of tubular and/or glomerular damage.

7.3.16 Renal function

Renal function will be assessed as serum creatinine and creatinine clearance calculated according to Schwartz formula. Both parameters will be determined at each scheduled study visit (V1 to V15) and weekly (\pm 7 days) during the first month after initiation or modification of therapy.

Serum creatinine for checking exclusion criteria must be assessed in duplicate between day -9 and day -7 of the screening period.

7.3.17 Haemoglobin

Haemoglobin level will be monitored at each scheduled study visit (V1 to V15). Haemoglobin level for checking exclusion criteria must be assessed between day -9 and day -7 of the screening period.

7.3.18 Neutrophil count and Neutropenia management

The measurement of absolute neutrophil counts will be done weekly (\pm 7 days), possibly at each scheduled visit for an early identification of cases of neutropenia and agranulocytosis. In case of infection neutrophil count should be monitored more frequently. Neutrophil count for checking exclusion criteria must be assessed between day -9 and day -7 of the screening period.

Neutropenia is defined as any ANC < 1500/mm³ confirmed in two consecutive measurements. If both consecutive counts are below $1.5 \times 10^9/L$ but are not within the same range, a third count is required to determine the severity category. Neutropenia is considered to be resolved when ANC is $\geq 1.5 \times 10^9/L$ on 2 consecutive counts.

Mild Neutropenia* (ANC $\geq 1000/mm^3$ and < $1500/mm^3$ in two consecutive measurements)

Moderate Neutropenia* (ANC $\geq 500/mm^3$ and < $1000/mm^3$ in two consecutive measurements)

Severe Neutropenia/Agranulocytosis* (ANC < $500/mm^3$)

The handling and follow up of the patient will depend on the severity of the neutropenia (mild, moderate, severe/agranulocytosis) as follows.

Mild Neutropenia:

- treatment must be interrupted and patient's ANC must be monitored every 1-3 days, or more frequently, until resolution of the event, defined as two consecutive ANC $\geq 1500/\text{mm}^3$.
- If the patient has a mild neutropenia and develops signs of infection (fever), therapy must be interrupted immediately and ANC must be obtained and monitored every 1-2 days, or more frequently, until resolution of the event.
- Provide protective isolation; treat the patient as per clinical need and per local protocol (antibiotic therapy, admission to hospital if clinically indicated). If possible, hemoculture, throat swab, viral studies (CMV, parvovirus, hepatitis A/B/C), serum ALT, BUN, creatinine will be collected.
- Therapy with DFP or DFX and continuation of trial can be restarted once all symptoms have been resolved and when it is deemed safe by the Investigator, after having consulted the Coordinating Investigator, in accordance with Table 4, Section 6.3 "Dose Adjustment".

Moderate Neutropenia

- treatment must be interrupted and the patient must be withdrawn from the study and monitored until resolution of the event;
- provide protective isolation; if clinically indicated, admit patient to hospital, obtain regular vital signs and treat the patient as per clinical need and per local protocol (antibiotic therapy and/or granulocyte colony stimulating factor).
- the patient will be examined the same day, if possible, collecting drug history and physical examination;
- if possible, hemoculture, viral studies (CMV, parvovirus, hepatitis A/B/C), serum ALT, BUN, creatinine will be collected.

Severe Neutropenia/Agranulocytos

- treatment must be interrupted immediately and the patient must be withdrawn from the study and monitored until resolution of the event;
- provide protective isolation; if clinically indicated, admit patient to hospital, obtain regular vital signs and administer appropriate therapy such as antibiotic therapy and granulocyte colony stimulating factor, beginning the same day that the event is identified;
- the patient will be examined the same day, if possible, collecting drug history and physical examination;
- if possible, hemoculture, viral studies (CMV, parvovirus, hepatitis A/B/C), serum ALT, BUN, creatinine will be collected.
- the patient will be monitored daily or more frequently until two successive ANCs are $\geq 1500/\text{mm}^3$.

All neutropenia, irrespective of their severity or seriousness must follow the expedite reporting of SAE, as indicated in Section 16.6 “Instructions for rapid notification of Neutropenia”.

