6.3 Dose Adjustments

Dose adjustments for both DFP and DFX will be allowed for efficacy reasons (scaling up) or for safety reasons including the presence of markers indicative of over-chelation (scaling down).

DFP can be scaled up in steps of 12.5 mg/kg/day (to a maximum daily dose of 100 mg/kg) according to the individual patient's response defined as an increase of serum ferritin levels > 20% compared to the previous determination.

DFX will be scaled up in steps of 5 to 10 mg/kg (to a maximum daily dose of 40 mg/kg) according to the individual patient's response defined as an increase of ferritin levels > 20% compared to the previous determination.

For patients with a stable serum ferritin value >1500 (no increase or any increase <20%) and not showing a downtrend over a 3-month-period , DFP or DFX can be also increased.

DFP and DFX must be scaled down for the safety reasons detailed in **Table 4**.

Table 4. Scale down adjustment for DFP and DFX (safety reasons)

Serum creatinine increased by >33% from baseline OR Reduction in creatinine clearance (estimated with the Schwartz formula) ≤ 90ml/min and >60 ml/min in two consecutive measurements	No dose adjustment.	Reduce DFX in steps of 10 mg/kg/day until value returns to baseline value and continue DFX with the adjusted dose for 1 month. If the increase persists interrupt DFX. If after DFX interruption value returns to baseline value or > 90 ml/min for creatinine clearance restart DFX at 50% of the last dose and then escalate by 10 mg/kg/day at 1 month intervals provided that value increase does not recur. Monitor serum creatinine, creatinine clearance and urine protein/creatinine ratio weekly (+/- 7 days) during the period of abnormal value and during the first month after dose modification, then monthly.
Urine protein/creatinine ratio ≥ 0.5 in two consecutive measurements	No dose adjustment.	Reduce DFX in steps of 10 mg/kg/day until value returns to < 0.5. If the increase persists interrupt DFX. After the ratio improves, restart DFX at 50% of the last dose and then escalate by 10 mg/kg/day at 1 month intervals provided that value increase does not recur. Monitor serum creatinine, creatinine clearance and urine protein/creatinine ratio weekly (+/- 7 days) during the period of abnormal value and during the first month after dose modification, then monthly.

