ALT or AST > 10 ULN	Interrupt DFP. When levels return to < 5 ULN, restart DFP at 50% of the last dose and after 1 month scale it back up to the former dose.	Interrupt DFX. When levels return to < 5 ULN, restart DFX at 50% of the last dose and then escalate by 10 mg/kg/day at 1 month intervals provided that value increase does not recur.

CONFIDENTIAL

Severe skin rash	No dose adjustment.	Interrupt DFX . Once resolved, restart DFX at 50% of the last dose and then escalate by 5 mg/kg/day at two-weeks intervals.
Ferritin \leq 500 ng/ml	Reduce DFP to 50% of last dose. If ferritin is still <500 ng/ml at subsequent monthly evaluation, DFP may continue having consulted the Coordinating Investigator. When value returns > 500 ng/ml DFP can be scaled up to full dose.	Reduce DFX to 50% of last dose. If ferritin is still <500 ng/ml at subsequent monthly evaluation, DFX may continue having consulted the Coordinating Investigator. When value returns > 500 ng/ml restart DFX at 50% of the last dose and then escalate by 10 mg/kg/day at 1 month intervals.
Neutropenia(neutrophil count $<1500/\text{mm}^3$ and $\geq 1000/\text{mm}^3$ in two consecutive measurements)*	Interrupt DFP and monitor neutrophil count every 1-3 days or more frequently. When value returns $> 1500/\text{mm}^3$ for two consecutive measurements, and if deemed safe by the investigator, restart DFP at the last dose after having consulted the Coordinating Investigator.	Interrupt DFX and monitor neutrophil count every 1-3 days or more frequently. When value returns $> 1500/\text{mm}^3$ for two consecutive measurements, and if deemed safe by the investigator, restart DFX at the last dose after having consulted the Coordinating Investigator.
Moderate Neutropenia (neutrophil count $<1000/\text{mm}^3$ and $> 500/\text{mm}^3$) OR Severe Neutropenia/Agranulocytosis (neutrophil count $< 500/\text{mm}^3$) Infection	Interrupt DFP. Exit from the protocol.	Interrupt DFX. Exit from the protocol.

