20. BENEFIT RISK ASSESSMENT

Risks

By participating in this research it is possible that the patients may experience some distress, even if the procedures foreseen in this trial are quite similar to those required for a well management of patients affected by hereditary haemoglobinopathies requiring chronic transfusions. Patients are submitted monthly to blood samplings and have to undergo MRI examinations three times during the 1 year period of treatment (at baseline, at month 6 and at month 12). The duration of MRI tests is higher at baseline and at the end of treatment since both cardiac and liver compartments have to be investigated.

Every measure to prevent distress and discomfort will be put in place. Blood samplings will be performed with butterfly needles at least in younger children or in children showing anxiety and distress. Moreover, monthly sampling will be planned to coincide as much as possible with the day of blood transfusion to which the patient must regularly undergo for the underlying disease.

Concerning MRI, for ethical reasons, the examinations are foreseen only in children for whom sedation is not required. Besides distress related to the procedure, some discomfort may however be experienced by patients referring to clinical centers not equipped for performing MRI examinations. These patients will be moved to the closest centre able to perform the MRI scan. Even if the costs for these displacements are covered by the study, patients may find some logistics difficulties impacting on their life and health.

Finally, during the course of the study patients could experience AEs following the use of both the experimental drug and the active comparator. Every effort will be made both by the medical investigator and by the sponsor to ensure appropriate monitoring of safety/tolerability and suitable measures will be put in place to handle and mitigate AEs.

Benefits

Patients enrolled in this trial are offered the opportunity to benefit from an oral chelator to treat their iron overload, thus improving treatment compliance and ultimately treatment efficacy.

For children randomized to the experimental arm, the use of a new strength (80mg/mL) of the currently marketed DFP oral solution will allow a more precise administration of the right dose according to the weight to the child. For those patients randomized to the control group the costs for the comparator

CONFIDENTIAL

DEEP Consortium

DEEP2-Efficacy/Safety Study Protocol

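### The weekly neutrophil count has a ±7-day window, so adjacent compliant counts can be up to 21 days apart, and the confirmatory count after a first result of 1000–1499/mm³ has no time limit

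*Combined protocol and SAP*

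**What the plan says.** **Frequency.** Section 7.3.18 sets neutrophil counts "weekly (\pm 7 days), possibly at each scheduled visit for an early identification of cases of neutropenia and agranulocytosis". Table 5 footnote 6 makes weekly counting mandatory from the start of treatment and ties the seven-day tolerance to the scheduled date. Section 7.2 gives the monthly visits ±7 days as well.

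**Confirmation.** Section 7.3.18: "Neutropenia is defined as any ANC < 1500/mm³ confirmed in two consecutive measurements". The mild row of Table 4 (Section 6.3) has the same trigger: "Neutropenia(neutrophil count $<1500/\text{mm}^3$ and $\geq 1000/\text{mm}^3$ in two consecutive measurements". Its action is "Interrupt DFP and monitor neutrophil count every 1-3 days or more frequently", with matching text for DFX. Section 16.6 starts rapid notification from the same two-count definition.

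**Other severity bands.** In Section 7.3.18 the moderate category (500–999/mm³) requires two consecutive counts; the moderate row of Table 4 states no such condition. The severe category (<500/mm³) carries no two-count condition in either place, and Section 7.3.18 has treatment interrupted at once. The same section asks for more frequent counts in infection, without giving an interval.

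**Renal tests.** Table 5 footnote 5 and Sections 7.3.15 and 7.3.16 put ±7 days on weekly creatinine and urine-protein tests in the first month. Table 4 repeats it for abnormal values: "weekly (+/- 7 days) during the period of abnormal value and during the first month after dose modification, then monthly".

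**Burden.** Section 20: "Patients are submitted monthly to blood samplings".

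**The concern.** A tolerance as long as the interval leaves the interval undefined. A site can meet the wording while two neighbouring counts are three weeks apart or on the same day. Weekly counting exists to find neutropenia early, and Section 8 names DFP-induced neutropenia as a risk.

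The window matters most after a first low count in the mild band. Every protective step there depends on a second consecutive count, and only the weekly schedule says when that count is due. If the schedule stretches, so does the time on drug before the protocol's own response begins.

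**Working it through.** The plan states no figure to reproduce. The check is schedule arithmetic followed by a comparison of the sections.

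**Inputs.** Interval I = 7 days and tolerance w = 7 days (Section 7.3.18); tolerance measured from the scheduled date (Table 5 footnote 6); two consecutive counts to confirm (Section 7.3.18, Table 4, Section 16.6); no time limit for the second count anywhere in the protocol.

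**Gap between adjacent counts.** Count k is due on day 7k and may be taken from day 7k − 7 to day 7k + 7.
- Longest gap = (7(k+1) + 7) − (7k − 7) = I + 2w = 7 + 14 = 21 days, three times the stated interval.
- Lower limit = I − 2w = 7 − 14 = −7 days. The windows overlap, so both counts can fall on one day or in reverse order.
- Enumerating the permitted offsets for two counts, and a brute-force search over seven weekly counts with offsets of −7, 0 and +7 days, also gave a maximum of 21 days.
- If the tolerance ran from the previous count, the maximum would be I + w = 14 days. Footnote 6 does not read that way.

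The monthly visits do not shorten the maximum, since they carry ±7 days too.

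**When a third count is needed.** Section 7.3.18 asks for one if two low counts fall in different bands. Three scheduled counts can then span 2I + 2w = 14 + 14 = 28 days.

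**Dosing between the first and second low count, by band.**
- *1000–1499/mm³:* Section 7.3.18 and Table 4 both act after two consecutive counts. The 1–3-day monitoring is part of the interruption step, so it starts after confirmation, and notification under Section 16.6 also waits. Nothing says whether dosing continues meanwhile. The text permits up to 21 days.
- *500–999/mm³:* the same delay is possible under Section 7.3.18. Under Table 4 as written, one count suffices. The two conflict.
- *<500/mm³:* no two-count condition in the category, so the delay does not arise.
- *Infection:* counts are to be more frequent, so the 21-day figure does not apply.

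**Renal tests.** A first on-treatment creatinine due on day 7 may be taken on day 7 + 7 = 14, and adjacent weekly tests may again be 21 days apart. Table 4's creatinine-clearance and urine-protein triggers also need two consecutive measurements.

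**The case against.** **Investigators will repeat a low count promptly, and nothing forbids it.** True, and 21 days is an extreme: one count a week early, the next a week late, with neighbouring counts bunched around them. But an early repeat is left to judgement; the protocol does not require it. The Study Procedures Manual or the monitoring plan may be tighter. Neither is available here, so it cannot be said that monitoring would fail to detect long gaps.

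Several stronger readings are tempting, and the documents do not support them:

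- *That dosing may continue for 21 days after any low count.* The unqualified general definition in Section 7.3.18 invites this. The severe category and the infection provision exclude it, and Table 4 does not support it for 500–999/mm³.
- *That a site may sample routinely every three weeks.* Eighteen dates would cover 52 weekly windows (52/3 = 17.3, rounded up), but only if one draw may serve every window it falls in. Nothing allows that, and footnote 6 makes weekly counts mandatory.
- *That 12 counts at the monthly visits would suffice.* The phrase about scheduled visits follows the weekly requirement and most naturally means combining a count with a visit where possible. It is unclear, but it is not an alternative schedule.
- *That neutropenia incidence would reflect sampling interval instead of drug.* Sampling interval can affect detection. The same schedule applies to both arms, however, and differential detection is not shown.
- *That Section 20 misinforms ethics committees.* It names no such audience. Its monthly statement is a separate inconsistency about burden and does not bear on the window arithmetic.

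The window–interval conflict and the untimed confirmatory count remain.

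**Conclusion.** The point holds in limited form. The ±7-day window equals the weekly interval, so adjacent compliant counts may be anything from coincident to 21 days apart. This is a stated rule that works against its own purpose, not merely a missing detail. For a first count of 1000–1499/mm³, the text permits up to 21 days of dosing before interruption, closer monitoring and rapid notification begin. The 21 days rests on reading the tolerance from the scheduled date, as footnote 6 says, and on no earlier repeat being taken; it is a permitted maximum and says nothing about typical practice.

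Three related matters belong with it: the conflict over the moderate category, the same window on the renal tests, and the monthly description in Section 20.

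**What to change.** These sections must be reconciled. All values are for the sponsor's safety lead to set; none is proposed here.

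1. Make the window compatible with the stated interval in Table 5 footnotes 5 and 6, Sections 7.3.15, 7.3.16 and 7.3.18, and the Table 4 monitoring text.
2. Clarify what the reference to scheduled visits in Section 7.3.18 means.
3. State when the confirmatory count follows a first count below 1500/mm³ and what the dosing status is meanwhile, consistently across Section 7.3.18, Table 4 and Section 16.6.
4. Reconcile the moderate-neutropenia criterion between Section 7.3.18 and Table 4.
5. Reconcile Section 20 with the sampling schedule.

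The change is to protocol wording. The cost is more window deviations on record and possibly some off-schedule confirmatory counts, which would mean additional blood draws for some children.
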